### 8.2.2 Replacement Policy

A replacement subject may be enrolled if deemed appropriate by the Sponsor-Investigator. Up to 2 subjects may be replaced if they are not evaluable for the primary outcome.

### 8.2.3 Accrual estimates

Based on current estimates of the number of eligible subjects, we estimate approximately 2 subjects to accrue per month, and anticipate completing accrual to the first cohort within 12 months.

## 8.3 Interim Analyses and Stopping Rules

Each cohort will be stopped early for lack of safety, if the safety lead-in portion cannot be completed as outlined in the Study Design (Section 3).

The planned interim analysis for both futility and efficacy will be included based on group sequential design for the combination cohorts. 12 subjects (including the 6 subjects in safety lead-in) will be accrued at the dose level decided at safety lead-in. If there are one or fewer responses in these 12 subjects, the study will be stopped due to futility, and if there are 5 or more responses, the study will be stopped due to efficacy (one-sided alpha spending =0.0004). The final decision to terminate the cohort or continue accruing after these first 12 subjects will be based on discussion amongst members of the Joint Steering Committee, which is comprised of representatives for both Merck and the Sponsor.

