## 3 Study Design

### 3.1 Characteristics

This is an open-labeled, single center, phase II study, in which eligible subjects will be treated with pembrolizumab-based therapy. The treatment cohorts will be accrued concurrently once 6 patients are enrolled in Cohort A (see study schema). Subjects with advanced RCC (locally advanced or metastatic) in whom CN/MET is feasible are eligible for this study. Eligible subjects must also have evaluable pre-treatment tumor specimen adequate for analysis, or consent to tumor specimen collection prior to enrollment.

Subjects enrolled into Cohort A will receive pembrolizumab monotherapy (200 mg Q3W). The objective of this monotherapy cohort is to determine the safety of pembrolizumab in subjects with

advanced RCC undergoing CN/MET. Of particular interest are surgical complications. The first 6 subjects accrued to Cohort A will be evaluated in a safety lead-in for the safety of pembrolizumab prior to planned CN/MET. For the first 6 patients in the safety lead-in, if ≥2 subjects experience Grade IV and V surgical complications according to the Clavien-Dindo classification (Appendix 3), the study will be halted to accrual. Given the complexity of surgery, it will be difficult to attribute surgical complications to the preoperative administration of pembrolizumab. Thus, the occurrence of these events may not require an early end to the study, but will be discussed amongst members of the Joint Steering Committee, Merck, and the Sponsor to consider whether the study can re-open to accrual.

After 6 patients are enrolled into Cohort A, Cohort B will open to concurrent enrollment where subjects will receive pembrolizumab in combination with axitinib. The pembrolizumab-based combination for cohort C has not yet been determined. Cohort C will be determined by discussion between the Joint Steering Committee, Merck, and the Sponsor, based on emerging data regarding promising combination approaches.

Enrolled subjects will begin their assigned preoperative pembrolizumab-based therapy (200 mg Q3W). After 9 weeks (3 × 3-week cycles of treatment), subjects will be assessed for response per RECIST 1.1 criteria (Section 7.1). Subjects will then proceed as follows:

- Subjects who achieve CR during the preoperative treatment period and have locally advanced disease will proceed with CN.
- Subjects with PR/SD during the preoperative treatment period will proceed with CN/MET.

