### 5.1.2 Cohort B: Pembrolizumab + Axitinib

#### 5.1.2.1 Safety Lead-In

The first 6 subjects accrued to Cohort B will be evaluated to test the safety of the combination of pembrolizumab and axitinib. All 6 subjects in Cohort B will be followed for 28 days after surgery for excessive post-operative complications before additional subjects are enrolled to each combination cohort. If  $\leq 1$  subject experience Grade IV/V surgical complications per the Clavien-Dindo classification (Appendix 3), then 11 additional evaluable subjects will be accrued to the cohort. If  $\geq 2$  subjects experience Grade IV/V surgical complications, or if  $\geq 2$  subjects experience a delay in surgery beyond the specified 14-21 day window following the end of the preoperative treatment period (that is, 14-21 days from Cycle 3, Day 21; delays for scheduling, operating room scheduling or patient preference are not included), then the cohort will be halted to accrual, and the safety data reviewed to modify the protocol as appropriate, including changes in dose level

(Section 5.1). If the cohort is re-opened with a change in dose level, an additional 6 subjects will be accrued to evaluate safety. If  $\leq 1$  subject experience a Grade IV/V surgical complication, then 11 additional subjects will be accrued to the cohort at the reduced dose. If  $\geq 2$  subjects experience a Grade IV/V surgical complication, the cohort will be terminated for lack of safety. Therefore, a minimum of 4, and a maximum of 36 subjects may be accrued into Cohort B.

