## 8.2 Determination of Sample Size and Accrual Rate

### 8.2.1 Sample Size and Power Estimate

For the primary objective, there will be a binary classification. A subject will be considered to have a “positive response” if there is a  $\geq 2$ -fold increase (from pre- to post-treatment) in the number of TICCs, and a “negative response” if there is  $< 2$ -fold increase.

For Cohort A, with 12 subjects, if the true response rate is 30%, the 90% confidence interval of the response rate is (8%, 52%).

For each of the combination cohorts (cohorts B and C), the expanded part will be accrued based on group sequential design. In the first stage, 12 subjects (including the 6 subjects in safety lead-in) will be accrued at the dose level decided at safety lead in. If there are one or fewer responses in these 12 subjects, the study will be stopped due to futility, and if there are 5 or more responses,

the study will be stopped due to efficacy (one-sided alpha spending =0.0004). The final decision to terminate the cohort or continue accruing after these first 12 subjects will be based on discussion amongst members of the Joint Steering Committee, which is comprised of representatives for both Merck and the Sponsor. If accrual to the cohort is continued, additional subjects will be accrued for up to 36 evaluable subjects (or up to 30 if no dose reductions occur).

The null hypothesis of a 10% response rate will be rejected if 6 or more responses are observed in 30 subjects. This design yields a one-side type I error rate of 0.05 and power of 82.3% when the true response rate is 30%. Additionally, the first 6 subjects will be considered the “safety lead-in” for each cohort. If there are  $\geq 2$  DLTs in these first 6 subjects, then dose reduction will proceed as described in Section 5.1 and an additional 6 subjects will be accrued. The 6 subjects accrued as the safety lead-in are evaluable. Therefore, a minimum of 4, and a maximum of 36 subjects will be accrued to each pembrolizumab-based combination cohort.

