### 3.3 Review of Adverse Event Rates

If an increase in the frequency of Grade 3 or 4 adverse events (above the rate reported in the Investigator Brochure or package insert) is noted in the study, the Principal Investigator is responsible for notifying the DSMC via report at the time the increased rate is identified. The report will indicate if the incidence of adverse events observed in the study is above the range stated in the Investigator's Brochure or package insert.

If at any time the Principal Investigator stops enrollment or stops the study due to safety issues, the DSMC Chair (or Vice Chair) and DSMC Director must be notified within one business day.

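### Once a six-subject lead-in is passed, no numerical rule covers Grade IV/V surgical complications in any cohort, and the lead-in count alone passes a true 30% rate 42% of the time

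*Combined protocol and SAP*

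**What the plan says.** Section 8.3 states: "Each cohort will be stopped early for lack of safety, if the safety lead-in portion cannot be completed as outlined in the Study Design". It sets no other safety boundary. The 12-subject interim analysis in 8.2.1 and 8.3 has futility and efficacy limits on TIIC response only.

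The lead-in rules stand elsewhere. In Cohort B (5.1.2.1), "The first 6 subjects accrued to Cohort B will be evaluated to test the safety of the combination of pembrolizumab and axitinib". If no more than one "subject experience Grade IV/V surgical complications per the Clavien-Dindo classification (Appendix 3), then 11 additional evaluable subjects will be accrued to the cohort". Accrual halts if two or more have such complications, or if two or more "subjects experience a delay in surgery beyond the specified 14-21 day window following the end of the preoperative treatment period". For a cohort that was halted, "If the cohort is re-opened with a change in dose level, an additional 6 subjects will be accrued to evaluate safety", with the same complication limit. Sections 3.1 and 5.1.1 give Cohort A a trigger of two or more of six, and 5.1.1 adds the surgery-delay trigger. Section 8.2.1 adds a third: two or more "DLTs in these first 6 subjects, then dose reduction will proceed as described in Section 5.1 and an additional 6 subjects will be accrued".

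On the purpose of Cohort A, Section 3.1 says: "The objective of this monotherapy cohort is to determine the safety of pembrolizumab in subjects with" advanced disease having surgery. Safety is also a secondary objective of the trial (2.1.2).

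After the lead-in, Appendix 2 provides for DSMC authorisation to proceed, SAE review at six-weekly DSMC meetings, monthly Site Committee review of Grade 3-5 events, and a report if Grade 3 or 4 events become more frequent, "above the rate reported in the Investigator Brochure or package insert". Section 6.7 lists general termination criteria without numbers.

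**The concern.** Surgical complications are the safety question this design singles out, yet the last point at which a count of them decides anything is subject 6. Six subjects cannot separate a tolerable rate of life-threatening or fatal complications from a high one. If a lead-in passes by chance, the complications graded afterwards feed no decision rule.

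The nearest numerical comparator, in Appendix 2 section 3.3, is the drug's brochure or label. That is not a postoperative benchmark, and the sentence names Grades 3 and 4 only. For the axitinib combination, Section 1.2.2.1 cites Grade 3 or higher events in 76% of patients, so a surgical excess could sit unnoticed inside an overall AE rate.

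**Working it through.** **Inputs.** Lead-in of 6, pass at 0 or 1 (5.1.2.1; 3.1 and 5.1.1 for Cohort A). Cohort A maximum 12 (3.2). Combination cohort maximum 30, or 36 with a dose reduction (8.2.1). 5.1.2.1 instead adds 11 after a pass. The plan gives no acceptable or unacceptable complication rate and no operating characteristics for the lead-in, so there is no stated figure to reproduce. The true rates p below are assumptions. The 30% in 8.2.1 is a TIIC response rate and is unrelated.

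**Step 1: chance of passing on the complication count.** P(pass) = (1−p)^6 + 6p(1−p)^5. At p = 0.30: 0.1176 + 0.3025 = 0.420.

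| True rate | 10% | 15% | 20% | 25% | 30% | 40% |
|---|---|---|---|---|---|---|
| Passes | 89% | 78% | 66% | 53% | 42% | 23% |

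**Step 2: effect of the other lead-in rules.** With an independent surgery-delay rate d, multiply by the chance of at most one delay in six. At p = 0.30 this gives 0.406 (d = 5%), 0.372 (10%) and 0.275 (20%). In the other direction, a halted Cohort B that re-opens is tested again. If the rate were unchanged, the chance of passing one of the two lead-ins on the complication count would be 0.420 + 0.580 × 0.420 = 0.664.

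**Step 3: what a pass excludes.** The exact one-sided 95% upper bound is 1 − 0.05^(1/6) = 39% after 0 of 6. After 1 of 6 it is 58%, the solution of (1−p)^6 + 6p(1−p)^5 = 0.05.

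**Step 4: subjects still to come.** Combination cohort under 8.2.1: 30 − 6 = 24, or 36 − 12 = 24. Under 5.1.2.1: 11. Cohort A: 12 − 6 = 6. At a true 30%, the expected Grade IV/V events in those subjects are 7.2, 3.3 and 1.8.

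**Step 5: an illustrative cumulative rule.** Halt for review at 2 of 6, 4 of 12, 5 of 18 or 6 of 24. With S_n the cumulative count, P(halt) = 1 − P(S6 ≤ 1, S12 ≤ 3, S18 ≤ 4, S24 ≤ 5), by exact enumeration with immediate outcomes and no TIIC stop. At p = 0.30 the four looks contribute 0.580 + 0.086 + 0.108 + 0.077 = 0.850, allowing for rounding.

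| True rate | Lead-in only | Looks at 6 and 12 (cap 17) | Looks at 6, 12, 18, 24 |
|---|---|---|---|
| 10% | 11.4% | 12.1% | 13.5% |
| 15% | 22% | 24% | 31% |
| 20% | 34% | 39% | 51% |
| 25% | 47% | 53% | 71% |
| 30% | 58% | 67% | 85% |

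**Step 6: lag.** 9 weeks of treatment, 2 to 3 weeks to surgery and 28 days of follow-up make about 15 to 16 weeks. At 2 subjects a month (8.2.3), about 7 more could enrol before a look matures if all entered one cohort.

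**The case against.** The plan is not without safety oversight. Life-threatening events and deaths are SAEs and go to the DSMC, all Grade 3-5 events are reviewed monthly, and deaths related to drug or procedure are notified within one business day. A six-subject gate followed by judgement is a recognisable design choice. A reader might infer that nothing could stop a cohort however many events followed. The documents do not support that: Appendix 2 and Section 6.7 leave room to stop, only without a threshold.

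A reader might also infer that the complication count alone settles the lead-in. It does not: surgery delays, DLTs and DSMC authorisation also count, so 42% is an upper limit for passing a single lead-in. The DLT trigger is hard to credit, however, because the available text does not define a DLT. The authorisation request follows completion of lead-in enrolment, and the lead-in audit covers visits through the first cycle, whereas surgery comes after three.

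Three further objections stand in part:

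- The gain depends on cohort size: with 17 subjects the looks at 18 and 24 never happen.
- Going past 12 needs 2 to 4 TIIC responses of 12 (34% likely at a 10% TIIC rate, 64% at 30%), subject to the steering committee's discretion.
- At true rates of 15% to 20%, which the team might find tolerable, the illustrative boundaries add noticeably to pauses. Section 1.3.1 reports no apparent increase in overall surgical morbidity or mortality with perioperative therapy.

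**Conclusion.** The gap is real. After a passed lead-in, no numerical surgical-safety rule applies in any cohort, and the lead-in's complication count would pass a true 25% rate about as often as not (53%) and a true 30% rate 42% of the time, or about 28% to 41% with independent delay rates of 20% down to 5%.

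It would be too strong to say that every cohort could then add 24 subjects. That holds only for combination cohorts under 8.2.1. Cohort A can add 6, and 5.1.2.1 says 11, a contradiction that must be reconciled. Nor does the plan claim that a passed lead-in demonstrates safety; it permits expansion.

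The pass probabilities are exact for the assumed rates. The gains from later looks also rest on immediate outcomes, no TIIC stop, and every enrolled subject being operated on. This is a worthwhile, inexpensive improvement, not a flaw that invalidates the design.

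**What to change.** In 8.3, add a cumulative count of Grade IV/V Clavien-Dindo complications among operated subjects in each combination cohort. Keep the existing trigger at 6. Repeat the count at the 12-subject look and, if the cohort goes to 30 or 36, at about 18 and 24. Crossing leads to the accrual halt and safety review already in 5.1.2.1. The team should set the acceptable and unacceptable rates, tune the boundaries to them, and state the operating characteristics, including how the 15 to 16 week lag is handled. The boundaries 2/6, 4/12, 5/18 and 6/24 are only an illustration.

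Reconcile the 11 additional subjects in 5.1.2.1 with the 30 or 36 in 8.2.1 first, because the number of looks depends on it. For every cohort, including Cohort A, report the Grade IV/V rate with its exact one-sided 95% upper bound.

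The cost is protocol wording, with no added subjects or visits, since complications are already graded and SAEs already reach the DSMC. The downside is more pauses at rates that may be acceptable (Step 5 table), and either waiting for outcomes or accepting that several subjects enrol before each look matures.

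### Stopping for efficacy at 5 or more responses in 12 carries a one-sided alpha of 0.0043 under the 10% null, not the stated 0.0004

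*Combined protocol and SAP*

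**What the plan says.** The statistical section of the protocol defines a two-look group sequential rule for each combination cohort.

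- Endpoint (section 8.2.1): "For the primary objective, there will be a binary classification". A subject responds or does not, according to a two-fold rise in tumor-infiltrating immune cells.
- Interim sample (section 8.3): "12 subjects (including the 6 subjects in safety lead-in) will be accrued at the dose level decided at safety lead-in".
- Interim futility (section 8.3): "If there are one or fewer responses in these 12 subjects, the study will be stopped due to futility".
- Interim efficacy (section 8.3): "if there are 5 or more responses, the study will be stopped due to efficacy (one-sided alpha spending =0.0004". Section 8.2.1 gives the same boundary and the same figure: "the study will be stopped due to efficacy (one-sided alpha spending =0.0004".
- Final test (section 8.2.1): "The null hypothesis of a 10% response rate will be rejected if 6 or more responses are observed in 30 subjects".
- Operating characteristics (section 8.2.1): "This design yields a one-side type I error rate of 0.05 and power of 82.3% when the true response rate is 30" percent.
- Maximum size (section 8.2.1): "additional subjects will be accrued for up to 36 evaluable subjects (or up to 30 if no dose reductions occur".

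Both sections leave the final decision after the first 12 subjects to the Joint Steering Committee. Neither names a spending function.

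**The concern.** With a binary endpoint, a 10% null and a count boundary in 12 subjects, the alpha used at the interim look is fixed by the binomial distribution. Five responses in 12 is an observed rate of 42%. That is unlikely under a 10% null, but not as unlikely as 4 in 10,000.

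The figure matters because it is the only error probability the plan attaches to an early efficacy stop. A committee weighing 5 of 12 would read it as a chance of 1 in 2,500 under the null (1/0.0004), when the rule gives about 1 in 231 (1/0.00433). A report of an early stop could repeat the wrong figure.

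**Working it through.** **Inputs.** Interim n = 12 and efficacy boundary 5 or more (8.2.1, 8.3); futility boundary 1 or fewer (8.2.1, 8.3); null rate 0.10, alternative 0.30, final rule 6 or more of 30, overall one-sided 0.05, power 82.3% (8.2.1).

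**Step 1: try to reproduce 0.0004.** Under the null, X ~ Binomial(12, 0.10), and the alpha used at the look is the sum over k = 5 to 12 of C(12,k) × 0.1^k × 0.9^(12−k).

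| k | Probability |
|---|---|
| 5 | 792 × 0.1^5 × 0.9^7 = 0.003788 |
| 6 | 924 × 0.1^6 × 0.9^6 = 0.000491 |
| 7 | 792 × 0.1^7 × 0.9^5 = 0.000047 |
| 8 to 12 | 0.000003 |
| **Total** | **0.00433** |

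The stated figure is not reproduced. The ratio is 0.00433/0.0004 = 10.8. As a share of the 0.05 level, the look uses 8.7% (0.00433/0.05) rather than 0.8% (0.0004/0.05). A simulation of 4 million draws also gives 0.0043.

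**Step 2: neighbouring boundaries.**

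| Boundary in 12 | Exact one-sided alpha at 10% |
|---|---|
| 4 or more | 0.0256 |
| 5 or more | 0.0043 |
| 6 or more | 0.00054 |
| 7 or more | 0.00005 |

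None equals 0.0004.

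**Step 3: other routes to 0.0004.** The normal approximation for 5 of 12 gives 0.00013 (null variance), 0.00075 (null variance, continuity-corrected) or 0.0130 (estimated variance). An O'Brien-Fleming-type spending function, 2 × [1 − Φ(z(1−α/2)/√t)], at t = 12/30 = 0.40 gives 0.0019 for the plan's one-sided 0.05. It gives 0.00039 only for one-sided 0.025.

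**Step 4: effect on the whole design.** The written rule stops at 1 or fewer or at 5 or more of 12, and otherwise rejects at 6 or more of 30. With binding futility:

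P(reject) = P(X ≥ 5) + sum over x = 2 to 4 of P(X = x) × P(Y ≥ 6 − x), with Y ~ Binomial(18, p).

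At p = 0.10:

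- x = 2: 0.2301 × 0.0982 = 0.0226
- x = 3: 0.0852 × 0.2662 = 0.0227
- x = 4: 0.0213 × 0.5497 = 0.0117
- Adding 0.0043 for the interim stop gives 0.0613.

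The same formula at p = 0.30 gives power of 87.0%. The variants are:

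| Final rule 6 of 30 | Type I error | Power at 30% |
|---|---|---|
| Efficacy stop at 5 of 12, binding futility | 0.0613 | 87.0% |
| Efficacy stop at 6 of 12, binding futility | 0.0608 | 86.9% |
| No efficacy stop, binding futility | 0.0608 | 86.9% |
| Efficacy stop at 5 of 12, non-binding futility | 0.0738 | 92.4% |

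The efficacy look therefore adds about 0.0006 to the overall error. Most null paths that reach 5 of 12 would also reach 6 of 30. The excess over 0.05 comes from the final boundary and is there without any efficacy look. The stated 0.05 and 82.3% are not reproduced in any row.

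**The case against.** The strongest defence is that an alpha spend in a group sequential design can be the amount a spending function allots at a given information fraction, rather than the exact size of a discrete boundary. An O'Brien-Fleming-type function at 12/30 with one-sided 0.025 gives 0.00039, and a normal approximation at that level puts the cut-off at about 4.7 responses, rounded up to 5. That may well be where the number came from, though this is inference. It does not rescue the text. The plan states a one-sided level of 0.05, for which the same function gives 0.0019. On this reading too, the 5-of-12 rule uses about 11 times its allotment, so figure and boundary still disagree.

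What stands is that the documents do not show which of the two was intended. If the spend was the fixed point, the boundary is what fails. Moving to 6 of 12 (0.00054) would come close to 0.0004 but would not meet it; the first boundary at or below that value is 7 of 12 (0.00005).

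Two further objections are fair. The practical effect of the interim error is small, because the trigger is a count and the committee has discretion. That limits the consequence but does not make the figure right. And the overall 0.05 and 82.3% are a separate matter, driven by the final 6-of-30 boundary. They should not add weight to the interim point, but they belong in the same edit because they sit in the same section and describe the same design.

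**Conclusion.** The concern holds. Under the plan's own 10% null, the interim efficacy boundary has a one-sided alpha of 0.0043, and the stated 0.0004 understates it by a factor of 10.8. The interim result rests only on the exact binomial with 12 evaluable subjects. It does not depend on whether the cohort later goes to 30 or 36, on whether futility is binding, or on what the committee decides.

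This is a reporting error worth correcting, with limited reach. It changes no decision rule, 0.0043 is well below 0.05, and the look contributes about 0.0006 to the overall error. The whole-design figures (0.0613 and 87.0%) assume a final analysis at 30 subjects with the boundaries followed as written and futility binding; with non-binding futility they are 0.0738 and 92.4%.

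**What to change.** - In sections 8.2.1 and 8.3, replace 0.0004 with 0.0043 and keep the boundary at 5 or more of 12.
- Only if a spend near 0.0005 was intended, change the boundary to 6 or more of 12 and state 0.0005. With the final rule of 6 of 30 and binding futility, this moves type I error from 0.0613 to 0.0608 and power from 87.0% to 86.9%.
- If a spending function was used, name it with its overall alpha, and give the exact probability of the boundary beside it.
- In section 8.2.1, state whether futility is binding and recompute the overall type I error and power: 0.061 and 87.0% if binding, 0.074 and 92.4% if not.

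The cost is one number in two places and one recomputed sentence. Correcting the interim figure needs no change to boundary or sample size. If the sponsor wants the overall error held at 0.05, the final boundary would need its own review, because the interim correction does not achieve that.
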